8.2.4 Randomization

During the procedure, when one or more inclusion criteria have been met AND it has been determined that none of the exclusion criteria are present, AND the papilla (major or minor depending on indication) has been visualized and deemed accessible, the subject will be randomized to receive a 100 mg of rectal indomethacin (two 50mg suppositories) only or the combination of PSP and 100 mg of rectal indomethacin in a 1:1 fashion using a web-based electronic randomization system that will be accessed on a computer within the endoscopy suite. The randomization schedule will be generated centrally at the data coordinating center and will ensure treatment balance within site.

NOTE: SUBJECTS NOT MEETING ANY INCLUSION CRITERIA OR IDENTIFIED AS INELIGIBLE BASED ON EXCLUSION CRITERIA DURING THE ERCP WILL NOT BE RANDOMIZED.

- Subjects in whom the consent process is initiated but are not consented will be recorded in the Screen Failure Log along with the reason for eligibility exclusion or unwillingness to provide consent.
- Consented subjects who are not randomized will be recorded in the Screen Failure Log along with the reason for eligibility exclusion.
- Consented subjects not eligible for randomization will receive continued medical treatment per standard of care at each institution and appropriate details will be documented in the subject research record.

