5.0 ELIGIBILITY CRITERIA

5.1 Inclusion Criteria

Subjects must meet the following inclusion criteria to be eligible for enrollment into the trial:

Any patient undergoing ERCP in whom pancreatic stent placement is planned for the purpose of PEP prevention, is ≥ 18 years old, who provides informed consent, AND:

Has **one** of the following:

1. Clinical suspicion of or known sphincter of Oddi dysfunction
2. History of post-ERCP pancreatitis (at least one prior episode of pancreatitis after ERCP)
3. Pancreatic sphincterotomy
4. Pre-cut (access) sphincterotomy (including septotomy)

5. Difficult cannulation: cannulation duration ≥ 6 minutes (starting at time of initial papillary engagement with at least 25% of the time in contact with the papilla) AND/OR ≥ 6 cannulation attempts (defined as sustained contact with papilla lasting at least 1 second).
6. Short-duration (≤ 1 min) balloon dilation of an intact biliary sphincter.

Or has **at least 2** of the following:

7. Age < 50 years old & female gender
8. History of recurrent pancreatitis (at least 2 episodes)
9. ≥ 3 pancreatic injections
10. Pancreatic acinarization, defined as opacification of pancreatic parenchyma with ductal contrast injection
11. Pancreatic brush cytology

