7.2 Presentation of Informed Consent

Consent will be obtained by either the Principal Investigator or by individuals approved by the Principal Investigator and whose names and copy of their curriculum vitae have been submitted to the SDMC. The initial consent will be the most recent IRB/REB-approved version. During the consent process the objectives of the study, as well as the risks and benefits of enrolling will be explained in detail to potential subjects.

Informed consent will be obtained from subjects in the pre-procedure preparation area at the time of obtaining ERCP consent, as part of normal patient care at the institution. The Informed Consent process will be documented in the subject record to include a review of the trial, the informed consent document, and that subject questions were answered prior to signature of the consent. Subjects will receive a copy of the signed and dated informed consent document and the original signed and dated consent form will be placed in the subject record. Original informed consent documents will be maintained on-file at each participating center. Once consented and enrolled into the trial, subjects will be issued a unique code to be used on data collection forms and other research records throughout the duration of the trial. Consent to procure outside medical records will also be obtained from study subjects in the event they are admitted to an outside facility after the ERCP.

To maximize recruitment, all patients without exclusion criteria will be asked to consent for the study, even if they do not meet any pre-procedural inclusion criteria. This strategy will increase enrollment because a subset of subjects will only become eligible for the study on the basis of meeting one or more intra-procedural inclusion criteria.

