**9.3 Secondary Outcome Variable Analysis**

Analysis of the secondary outcome, the proportion of subjects with moderate-severe PEP, will be analyzed in a similar manner as the primary outcome.

We also will examine the impact of pre-specified characteristics on the primary and secondary outcomes. Specifically, the goal of this analysis is to examine prognostic variables and their impact on the primary analysis. We also will explore subgroup populations for future hypothesis generation. The baseline variables that will be examined are: age (continuous), gender, race, body mass index (continuous), suspicion of sphincter of Oddi dysfunction, prior post-ERCP pancreatitis, history of recurrent pancreatitis, manometrically documented sphincter of Oddi dysfunction, difficult cannulation, pre-cut (access) sphincterotomy, pancreatic sphincterotomy, pancreatic acinarization, biliary sphincterotomy, pancreatic stent placement, double wire technique, make/model/length/caliber of pancreatic stent, trainee involvement, prophylactic stent characteristics, type of sphincter of Oddi dysfunction, and inpatient vs. outpatient status. The assessment of each of these variables will be conducted using a logistic regression model with the dichotomous primary outcome, PEP event. Treatment arm will be a main effect in the model and the above covariates examined. Each covariate will be assessed individually first with a model that includes interaction effect with the treatment. If a significant interaction is observed ( $p < 0.10$ ), then exploratory subgroup analyses will be considered. For each model, we will be looking at the parameter estimate of the covariate to examine its association with outcome. We also will be examining the parameter estimate of the treatment in the presence of the covariate. A multivariable model will be created based on the results of the individual models (a combination of statistical and clinical significance will be used for model inclusion). The final multivariable model will be based on goodness of fit criteria. For this final model, the adjusted risk difference will be estimated with a 95% confidence interval. If the upper limit of this confidence interval is 5% or greater, then non-inferiority of the treatments cannot be concluded in the presence of the particular covariates. This analysis will be run on both the ITT and PP analysis populations.

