For the multivariable model, it is possible that several of the baseline characteristics will be eligible for the model. In this case, we will derive a risk score based on the methods used in the previous indomethacin trial. Individual patient risk scores will be determined by assigning one point for each major inclusion criteria and 0.5 points for each minor inclusion criteria (see below table). Similar to the above methods, the derived risk score will be examined for inclusion in the final multivariable model. In addition to the risk score, we will use a propensity score approach to derive a baseline variable that describes the baseline risk. The results of each risk score approach will be compared to provide helpful information for future trials.

Major Risk Criteria (1pt each)	Minor Risk Criteria (0.5pts each)
Suspicion of SOD	Age < 50
Prior post-ERCP pancreatitis	Female gender
Difficult cannulation	History of recurrent pancreatitis
Pre-cut sphincterotomy	
Pancreatic sphincterotomy	

Several procedures have been incorporated into the study design (i.e., procedure manual, training, protocol violation monitoring, outcome adjudication) to reduce center effects; however, these effects should not be ignored for this trial. As a secondary analysis of the study outcomes, a two-sided confidence interval for the difference in the PEP event rate between the two treatment arms will be calculated using the Newcombe method, stratifying by site. Non-inferiority will be concluded if the upper limit of the confidence interval is less than 5%. Similar to the assessment of potential prognostic variables, the results of this secondary analysis will be taken into account when interpreting the final results of the trial.

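### SAP 9.3 treats cannulation and sphincterotomy events as baseline for everyone, although subjects eligible on history can be randomised before those events occur

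*Protocol*

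**What the plan says.** **When randomisation happens.** Protocol 8.2.4 requires at least one inclusion criterion, no exclusion, and then: "the papilla (major or minor depending on indication) has been visualized and deemed accessible, the subject will be randomized". Cannulation is not a condition.

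**Who can qualify before cannulation.** Protocol 5.1 accepts either of two history items alone: "Clinical suspicion of or known sphincter of Oddi dysfunction", or "History of post-ERCP pancreatitis (at least one prior episode of pancreatitis after ERCP". Criteria 7 and 8 together (a woman under 50 with recurrent pancreatitis) also suffice.

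**Who qualifies later.** Difficult cannulation is defined by attempts at the papilla or by time, with "cannulation duration ≥ 6 minutes (starting at time of initial papillary engagement", so it cannot exist until the papilla has been engaged. Protocol 7.2 expects that "a subset of subjects will only become eligible for the study on the basis of meeting one or more intra-procedural inclusion criteria".

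**What the SAP does with these events.** SAP 9.3 opens its covariate list with "The baseline variables that will be examined are: age (continuous), gender, race" and continues through "difficult cannulation, pre-cut (access) sphincterotomy, pancreatic sphincterotomy, pancreatic acinarization, biliary sphincterotomy". It then adds pancreatic stent placement, double-wire technique and stent characteristics. For the risk score, "Individual patient risk scores will be determined by assigning one point for each major inclusion criteria"; difficult cannulation, pre-cut and pancreatic sphincterotomy are three of the five major items. A propensity score for baseline risk is also planned. The adjusted risk difference is compared with 5%, and interactions at p < 0.10 may lead to subgroup analyses.

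**Who performs the procedure.** SAP 7 states that the ERCP team is unblinded. Protocol 8.2.3 leaves almost all components of the procedure other than the prophylactic stent to the endoscopist.

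**The concern.** A baseline covariate should be fixed before assignment. For subjects randomised on history, the procedural items in SAP 9.3 can arise after assignment, in the hands of an operator who knows whether a pancreatic stent is required. If the assignment changes how often these events occur, or how they are recorded, three things follow:

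- The adjusted risk difference no longer estimates the effect of assignment, because part of that effect may run through the covariate.
- Subgroups defined by the event are no longer randomised comparisons. Protocol 13.3 wants subgroups to suggest who may particularly benefit from a stent.
- The risk score mixes prior risk with consequences of assignment, and to a different degree by route of entry.

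An arm difference is plausible: only one arm requires entry to the pancreatic duct for a prophylactic stent, and Protocol 3.1 and 3.2 describe that instrumentation as contributing to pancreatitis. The protocol already guards against a similar hazard in 8.2.7, which requires the endoscopy team's intravenous fluid decisions to be made before randomisation. Nothing comparable is set for the SAP 9.3 covariates.

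**Working it through.** **1. Status of each item**

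| SAP 9.3 item | Inclusion criterion | Risk-score points | Fixed before cannulation? |
|---|---|---|---|
| Suspected sphincter of Oddi dysfunction | 1 | 1 | Yes |
| Prior PEP | 2 | 1 | Yes |
| Recurrent pancreatitis | 8 | 0.5 | Yes |
| Difficult cannulation | 5 | 1 | No |
| Pre-cut sphincterotomy | 4 | 1 | No |
| Pancreatic sphincterotomy | 3 | 1 | No |
| Acinarization | 10 | none | No |
| Biliary sphincterotomy | none | none | No |
| Double-wire technique | none | none | No |
| Stent placement and characteristics | none | none | No; belongs to the randomised treatment |

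The word baseline cannot be taken to mean before randomisation, because the same list includes the characteristics of the prophylactic stent.

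**2. The plan's own figure**

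The documents give no figure on this point. The primary power statement (SAP 4.2: 650 per arm, 9.7% in both arms, 5-point margin, one-sided 2.5%) reproduces:

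Φ(0.05 / √(2 × 0.097 × 0.903 / 650) − 1.96) = 86.1%, against 85% stated.

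That calculation uses no covariates and does not change.

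**3. Size of a possible shift**

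Let f be the share randomised before the event can occur, m_C and m_I the event rates in that share (combination, indomethacin alone), β the added PEP risk with the event, and d the difference not running through it. Then:

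- Unadjusted difference (alone − combination) ≈ d + f × (m_I − m_C) × β
- Difference adjusted for the event ≈ d
- Adjusted − unadjusted ≈ f × (m_C − m_I) × β

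None of f, m_C, m_I or β is in the documents. All values here are assumed.

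- f = 0.4, m_C − m_I = 0.10, β = 8 points: 0.4 × 0.10 × 8 = 0.32 points, upward.
- Low end: 0.2 × 0.05 × 5 = 0.05 points.
- High end: 0.6 × 0.20 × 10 = 1.2 points.
- m_C = m_I: zero.
- m_I > m_C: the same sizes, downward.

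**4. Simulation check**

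1090 per arm, 600 runs per row; PEP risk 5% in the combination arm without the event; event rate 70% in both arms among the remaining subjects; logistic model standardised to a risk difference. The last two columns give the share of runs with the upper 95% limit below 5%.

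| f | Event, alone v combination | β | d | Unadjusted | Adjusted | Below 5%, unadjusted | Below 5%, adjusted |
|---|---|---|---|---|---|---|---|
| 0.4 | 40% v 40% | 8 | 3 | 3.1 | 3.1 | 30% | 30% |
| 0.4 | 30% v 40% | 8 | 3 | 2.7 | 3.0 | 42% | 34% |
| 0.4 | 20% v 40% | 8 | 3 | 2.4 | 3.1 | 51% | 32% |
| 0.6 | 20% v 40% | 10 | 3 | 1.9 | 3.1 | 67% | 29% |
| 0.6 | 40% v 20% | 10 | 2 | 3.3 | 2.1 | 26% | 61% |

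The simulated shifts follow the formula. The adjusted and unadjusted results can disagree in either direction, but only when the event differs by arm.

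**The case against.** **The trial's claim does not rest on this model.** A reader might infer that the non-inferiority conclusion is biased. SAP 9.1 does not support that: the primary difference is unadjusted, and non-inferiority must hold in both the ITT and the per-protocol populations. The 5% statement in SAP 9.3 can only withhold a conclusion in the presence of the covariates; it cannot rescue a failed primary analysis. This objection stands and limits the point to secondary and exploratory work. That work still counts, since SAP 9.3 says such results will inform interpretation.

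**Direction.** A reader might infer that adjustment flatters indomethacin alone by hiding harm from stenting. The sign is the opposite. If the events are more frequent with combination therapy, adjustment raises the alone-minus-combination difference and makes the adjusted analysis stricter. A permissive shift needs the reverse imbalance, for which the documents give no argument.

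**Scale.** It is tempting to set the shift against the 2.3 points (12.0% − 9.7%) in SAP 4.1. That allowance belongs to the unadjusted comparison, and a shift in a secondary model uses none of it.

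**Timing and mechanism are inferred.** Protocol 8.2.4 nowhere says before cannulation, and its note expects some exclusions to be found during the ERCP, which may delay randomisation. The share eligible on history is not given. The background sections describe harm from stent placement; they do not say that assignment changes pre-cut, sphincterotomy or difficult cannulation. Protocol 8.2.6 collects stent deployment time and difficulty separately, so that effort need not count as difficult cannulation. All this is fair, and it makes the size uncertain. It does not turn an event after assignment into a baseline variable.

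**Conclusion.** The point holds as a defect of specification in SAP 9.3. For subjects randomised on history, the listed procedural items can be post-randomisation events under an unblinded operator, and nothing in either document limits them to their status at randomisation. Stent placement and characteristics are a plainer case, since they belong to the randomised treatment.

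The exposure is confined to the secondary adjusted risk difference and its 5% statement, the interaction tests and subgroups, and the risk and propensity scores. The primary ITT and per-protocol analyses and the sample size are untouched.

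The shift is about 0.3 points under the central assumptions and 0.05 to 1.2 points over the assumed range. It is upward if the events are more frequent with combination therapy, downward if the reverse, and zero if the arms do not differ. The documents do not show which of these applies.

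**What to change.** In SAP 9.3:

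1. Restrict covariates, interactions, subgroups, the risk score and the propensity score to items known before randomisation. For each intra-procedural item use its status at the moment of randomisation. State the rule explicitly for biliary sphincterotomy and double-wire technique, which are not inclusion criteria and so would not be captured by an eligibility check.
2. Report events first occurring after randomisation, together with stent placement and stent characteristics, descriptively by arm and not as baseline adjusters.
3. For future subjects, record at randomisation every criterion already met, not just one that qualifies the subject, and the status of the two items named above.
4. For subjects already randomised without timing data, use pre-procedural variables only, or the qualifying criteria recorded at entry. State which before the final analysis.

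**Cost.** SAP wording and a small added data item; Protocol 8.2.4 needs only one criterion to be confirmed, so full status may be new data. The covariates will explain somewhat less outcome variation. Subgroups will partly reflect route of entry, because a subject randomised early who later has a difficult cannulation counts as not having had it at randomisation. The report should say so.

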8.2.5 Indomethacin Administration

Indomethacin suppositories will be administered to subjects in both study groups by an endoscopy nurse, technician, or the endoscopist at the time of randomization during the ERCP. Rectal indomethacin was selected (as opposed to diclofenac) because it is approved by the FDA and Health Canada and commercially available in the United States and Canada. This dose of indomethacin is congruent with all prior studies evaluating rectal NSAIDs in PEP prevention, wherein a 100 mg dose of rectal NSAIDs is administered in the peri-procedural period. The rectal route was selected on the basis of available clinical data suggesting that only rectal NSAIDs are effective in PEP prophylaxis, perhaps due to more rapid and complete bioavailability. Several recent meta-analyses have confirmed the effectiveness of rectal NSAIDs for preventing post-ERCP pancreatitis, and existing practice guidelines recommend their use in all patients undergoing ERCP.

8.2.6 Pancreatic Stent Placement

Patients randomized to the PSP group will undergo stent placement at the appropriate time during the ERCP. The technique by which prophylactic pancreatic stents are placed and the type of stent used will not be directed by the study protocol but rather deferred to the judgment and expertise of the endoscopist. This approach is intended to mimic real-world practice, wherein variations in stent type, caliber, and length exist.¹⁸ Specific information regarding stent make/model, caliber, length, guidewire used, amount of time required for deployment, and difficulty of stent placement will be collected to allow exploratory analyses of how stent characteristics influence PEP risk. For cases in which a pancreatic stent is placed to facilitate biliary access (precut sphincterotomy over a stent) or pancreatic sphincterotomy, if the subject is randomized to the indomethacin alone group, the pancreatic stent will be removed before the termination of the case.

8.2.7 Intra-Procedural Intravenous Fluid Administration

Intravenous fluid (IVF) administration during the ERCP will be left to the discretion of the clinicians involved in the ERCP (attending endoscopist, trainee, anesthesia personnel). Since IVF type and rate may influence the development of the primary and secondary endpoints, all decisions regarding IVF administration made by the endoscopy team must be implemented prior to randomization. After randomization, unblinded study personnel should not recommend any changes in IVF administration. For example, an attending endoscopist may ask anesthesia personnel to increase the IVF rate once he/she determines that the case has become high risk due

to a difficult cannulation. However, no further changes can be recommended or made once randomization has occurred.

After randomization, urgent changes in IVF administration in response to hemodynamic instability or volume overload will be dictated by anesthesia personnel. All efforts should be made to ensure that these anesthesia personnel are not aware of the overall purpose of the study nor are they fully aware of study group assignment.

Specific information regarding IVF administration immediately before, during, and after the case will be collected in the CRF to allow exploratory analyses of how IVFs influence PEP risk.

8.2.8 Maintenance of the Blind

Since the endoscopist(s), endoscopy nurse, and technician/assistant involved in the ERCP will be aware of whether or not a stent was placed, these individuals **will not** be involved in the subsequent post-procedure care of the patient until at least 48 hours after the procedure, at which point the presence or absence of the primary endpoint (PEP) will have become apparent. This approach is critical to maintaining blinding (of patients, treating clinical personnel, and outcome assessors), which ensures equal co-interventions between study groups and unbiased adjudication of the primary outcome.

In order to ensure blinding of 1) subjects, 2) healthcare providers making clinical decisions that may directly impact the primary endpoint (e.g. rate of intravenous fluid administration, amount of analgesics delivered, decision to keep the patient in the hospital a second night), and 3) those who will adjudicate the study outcomes, the endoscopy report and medical record will NOT state whether a stent was placed. Instead, the following statement will be input into the endoscopy report:

“This patient was enrolled in study protocol #xxxxxx in which he/she was randomized to receive either a dose of indomethacin only or both indomethacin and a prophylactic pancreatic stent for the prevention of post-ERCP pancreatitis. If this patient received indomethacin and a stent, he/she will be contacted 1-4 weeks after the ERCP to arrange an abdominal XRAY that is necessary to ensure spontaneous passage of the pancreatic stent.”

If a stent was indeed placed, 1-4 weeks after the procedure, the endoscopist or their clinical support personnel will contact the subject and deliver a requisition for an abdominal XRAY. Ensuring that the XRAY is performed, following up on the results, and removing retained stents will be the responsibility of the treating endoscopist and his/her support staff, as per standard clinical protocols. Patients who receive this requisition will be unblinded to study group assignment although this will occur after the primary endpoint has been established. This unblinding could theoretically impact development or assessment of the secondary endpoint, although subjects will be **discouraged from mentioning** their randomization assignment to study personnel during the 30-day telephone visit.

We realize that a small fraction of study subjects will undergo abdominal imaging within the first 2 post-ERCP days, the results of which may provide the clinical care team with information pertaining to PSP. This is an unavoidable threat to blinding; however, we believe that this will occur in only a small percentage of enrolled subjects.

